#### **ASSIST**

The ASSIST will not be included in the inferential analysis of primary and secondary outcomes and instead summarised using descriptive statistics. For each substance, the total score for ASSIST will be summarised using mean and standard deviation by randomised group and timepoint.

#### **Analysis of app engagement**

We will report means and standard deviations by group for each of the four subscales of the QFQ: a) Ease of use b) Fit in daily life c) Acceptability, and d) Perceived helpfulness.

## **Analysis of health economic outcomes**

#### Actissist 2.0 Statistical Analysis Plan v1.0

The visual analogue scale from the EQ-5D-L will be analysed using a mixed effects model implemented in the same way as for the analysis of clinical outcomes. The five components for the EQ-5D-L will be summarised by treatment group and time point using the mean and standard deviation.

The CSRI will be summarised using descriptive statistics only. We will present the number and proportion of participants at each time point who have had:

- i. Hospital inpatient stay (at least overnight)
- ii. Outpatient appointment (4 hours or less)
- iii. Day appointment > 4 hours
- iv. Use of A&E

Other data collected as part of the CSRI will not be summarised as part of this analysis.

#### Missing data

#### Imputation and pro-rating

Missing data on individual measures will be pro-rated on a subscale level if more than 90% of the items of a subscale are completed; otherwise the measure will be considered as missing. Exceptions where this rule does not apply for PANSS and ISMI are given below. Missing values in baseline covariates will be handled using mean imputation – the missing value will be imputed with the mean of the covariate for all participants in the trial (20).

When follow up of PANSS was completed over the phone, item one on the negative subscale (N1) and 4 and 5 on the general subscale (G4, G5) were not completed as these items are based on observation. Where these items are missing, they will be prorated as the mean of the respective subscale. When this occurs no additional items will be prorated – if in addition to N1, G4, and G5 have not been completed the measure will be considered missing.

The questionnaire instructions for ISMI define the total score for the outcome as the mean of all completed items. For this scale we will calculate a score if any items have been completed.

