### 2. Outcome measures

## **Primary outcome**

The primary outcome is psychotic symptoms measured by PANSS total score at 12 weeks post randomisation(1).

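### The pro-rating rule cannot operate on subscales of 10 or fewer items, so one missing positive or negative item (other than N1) voids an in-person PANSS total

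*SAP*

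**What the plan says.** The SAP's section on imputation and pro-rating sets one general rule: "Missing data on individual measures will be pro-rated on a subscale level if more than 90% of the items of a subscale are completed". A subscale that falls short costs the whole score at that visit: "otherwise the measure will be considered as missing". The section then allows two departures: "Exceptions where this rule does not apply for PANSS and ISMI are given below".

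- **PANSS by phone.** At phone follow-ups "item one on the negative subscale (N1) and 4 and 5 on the general subscale (G4, G5) were not completed", because they are rated by observation. "Where these items are missing, they will be prorated as the mean of the respective subscale". The allowance is capped: "When this occurs no additional items will be prorated".
- **ISMI.** "For this scale we will calculate a score if any items have been completed".

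The scoring table in Appendix 2 gives the item counts and splits PANSS into 7 positive, 7 negative and 16 general items. PANSS matters most here: "The primary outcome is psychotic symptoms measured by PANSS total score at 12 weeks post randomisation".

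**The concern.** The text reads as a modest tolerance for the odd skipped item. On the item counts in Appendix 2, it gives no tolerance at all for two of the three PANSS subscales and for most of the short secondary scales. Four consequences follow.

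- A nearly complete in-person assessment of the primary outcome can be discarded over one item, although the plan accepts a less complete PANSS by phone. This sits awkwardly with the commitment in General analysis principles to use the data available from every participant.
- The lost score becomes missing data that rests on the missing-at-random assumption, when 29 of its 30 items were observed.
- The planned missing-data sensitivity analysis is not aimed at this loss. It selects predictors from a model of visit attendance, and a participant who attended but lost the total over one item counts as having attended.
- The rule is worded generally, so it appears to cover baseline too. A baseline PANSS with one such gap would be replaced by the trial mean.

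**Working it through.** **Inputs.** The threshold is strictly more than 90%, applied per subscale (Imputation and pro-rating). Item counts come from Appendix 2. The phone pattern is N1, G4 and G5 absent (Imputation and pro-rating). The plan states no figure of its own on this point, so there is none to reproduce.

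**Step 1: when can one gap be tolerated?** With n items and one missing, the rule needs (n − 1)/n > 0.90. That is 0.10 × n > 1, so n > 10. At n = 10 the share is exactly 90.0%, which is not more than 90%.

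**Step 2: apply this to the listed scales.**

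| Scale | Items | Complete with one missing | Most items that may be missing |
|---|---|---|---|
| PANSS positive | 7 | 6/7 = 85.7% | 0 |
| PANSS negative | 7 | 6/7 = 85.7% | 0 |
| PANSS general | 16 | 15/16 = 93.75% | 1 |
| PSYRATS delusions | 6 | 5/6 = 83.3% | 0 |
| PSYRATS hallucinations | 11 | 10/11 = 90.9% | 1 |
| CDSS | 9 | 8/9 = 88.9% | 0 |
| PCPW criticism | 4 | 3/4 = 75.0% | 0 |
| PCPW warmth | 3 | 2/3 = 66.7% | 0 |
| AUDIT | 10 | 9/10 = 90.0% | 0 |
| CUDIT-R | 8 | 7/8 = 87.5% | 0 |
| DUDIT-e readiness | 8 | 7/8 = 87.5% | 0 |
| QFQ scales | 4 to 6 | 75.0% to 83.3% | 0 |
| WEMWEBS | 14 | 13/14 = 92.9% | 1 |
| QPR | 15 | 14/15 = 93.3% | 1 |
| DUDIT-e positive, negative | 17 each | 16/17 = 94.1% | 1 each |
| ERS | 28 | 27/28 = 96.4% | 2 (26/28 = 92.9%) |

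**Step 3: compare two PANSS assessments.**

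- In person, one positive item missing: positive 6/7 = 85.7%, total 29/30 = 96.7%. The subscale fails the rule and the measure is missing.
- By phone, N1, G4 and G5 missing: negative 6/7 = 85.7%, general 14/16 = 87.5%, total 27/30 = 90.0%. Both affected subscales fail the general rule, but the exception keeps the score.

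**Step 4: could PANSS be treated as one 30-item scale?** One or two gaps would then pass (29/30 = 96.7%, 28/30 = 93.3%). The wording does not support this: the rule works by subscale, and the same section speaks of the negative and general subscales by name.

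**The case against.** The best defence is that a strict rule is not a wrong rule. It is pre-specified and reproducible, and requiring a short scale to be complete is a legitimate conservative choice. It does operate on seven of the longer scales. This stands: had the SAP simply said that short scales must be complete, there would be little to dispute.

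The phone exception is also reasoned. The three items need observation, so the gap is fixed by visit mode, and without the exception every phone PANSS would be lost. Phone visits get no general leniency: a missing positive item voids the PANSS in either mode, and a gap in any other general item is treated more strictly by phone than in person. A reader might infer arbitrary favour to phone visits, and the SAP does not support that. What remains is narrower: having accepted 6/7 negative items as a sufficient basis by phone, the plan gives no reason for rejecting 6/7 in person.

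Three stronger readings also go too far.

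- **All PANSS gaps are fatal.** A single general-item gap is pro-rated. A lone missing N1 may fall under the exception, since the text does not say whether that extends to in-person visits. The point holds for the 7 positive items and N2 to N7.
- **The participant is lost.** Only that visit's score is. A participant with a 24-week PANSS stays in the mixed model. Baseline gaps are less likely because eligibility depends on PANSS item scores.
- **A sizeable share of primary outcomes will go.** With assumed independent item-missingness of 0.2%, 0.5% or 1%, 1 − (1 − p)^14 over the 14 positive and negative items gives 2.8%, 6.8% or 13.1%. Nothing in the SAP anchors those rates or the independence, and trained assessors rate the scale. The true loss could be near zero.

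**Conclusion.** The point holds as a defect of design in the scoring rule. On the SAP's own item counts, the tolerance is inert for every subscale of 10 or fewer items, and at an in-person visit it voids a 96.7%-complete PANSS when the gap is a positive item or one of N2 to N7. The plan's own acceptance of 27/30 items by phone makes this more than a preference for a looser threshold.

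A reader might infer a biased treatment comparison. The documents do not show one: the rule is the same in both arms, and nothing suggests that item gaps differ between them. The cost is avoidable loss of precision, of unknown size because no item-missingness rate is given. The conclusion rests on reading the rule by subscale, as the SAP words it, and on the item counts in Appendix 2. It is worth changing because the primary outcome is affected and the change costs almost nothing.

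**What to change.** Reword the general rule in Imputation and pro-rating as three cases:

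- more than 10 items: pro-rate if more than 90% are completed, as now;
- 6 to 10 items: pro-rate when exactly one item is missing, otherwise treat as missing;
- 5 or fewer items: complete-only.

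Leave the phone and ISMI exceptions as written. For in-person PANSS this allows at most one missing item in each subscale, so 3 of 30 in total, the number the plan already accepts by phone. The least complete short scale would be PSYRATS delusions or the 6-item QFQ scale, at 5/6 = 83.3%.

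Simpler repairs work less well.

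- Changing the threshold to at least 90% would help only AUDIT.
- A blanket rule of at least 80% would admit 2 of 10 items, 5 of 28 on ERS (23/28 = 82.1%) and 1 + 1 + 3 = 5 of 30 on PANSS.
- Copying the phone allowance to in-person visits would still void a PANSS with one missing positive item.

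The cost is a wording change, and a few short-scale scores that rest on one pro-rated item. If complete-only scoring of short scales is in fact intended, the SAP should say so and explain why 6/7 negative items suffice by phone but not in person.

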#### Assumptions for primary analysis

The primary analysis assumes data are missing at random, conditional on the observed values of the outcome at baseline, and follow up, and other covariates in the model.

#### Sensitivity analysis

We will conduct a sensitivity analysis for the primary outcome to assess whether different assumptions about missing data lead to different results. The sensitivity analysis will be conducted using the same model as is used in the primary analysis with the addition of baseline variables found to be predictive of missingness. Baseline variables will be considered predictive of missingness if p < 0.05 in a univariate logistic regression model, with attending the visit as the outcome and the baseline variable of interest as the only predictor. This sensitivity analysis will assume data is missing at random conditional on the variables in the primary analysis model and variables that are found to be predictive of missingness.

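### The only missing-data sensitivity analysis varies the conditioning set under missing at random, so it cannot show the effect of missingness that depends on the unobserved 12-week PANSS

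*SAP*

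**What the plan says.** Three statements in SAP section 5, under Missing data, define the plan.

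- Assumption of the main model, stated under its own subheading: "The primary analysis assumes data are missing at random". The variables conditioned on are the PANSS values seen at baseline and at follow-up, plus the model's remaining covariates.
- Aim of the sensitivity analysis, given in the paragraph of that name: "We will conduct a sensitivity analysis for the primary outcome to assess whether different assumptions about missing data lead to different results".
- Method (same paragraph): it is run "using the same model as is used in the primary analysis with the addition of baseline variables found to be predictive of missingness". The selection rule is: "Baseline variables will be considered predictive of missingness if p < 0.05 in a univariate logistic regression model", with visit attendance as the outcome and one baseline variable at a time. The candidate variables are not listed. The paragraph then names its own assumption: "This sensitivity analysis will assume data is missing at random conditional on the variables in the primary analysis model" together with the selected predictors.

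The SAP contains no delta-adjusted, pattern-mixture, reference-based, selection-model or tipping-point analysis. The one other sensitivity analysis, under COVID-19 pandemic, is conditional on a t-test and drops observed 24-week data collected after 1 March 2020. It does not address missing 12-week PANSS, which is the primary outcome.

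**The concern.** The aim is worded broadly and the analysis is narrow. Adding baseline covariates can deal with missingness that measured baseline variables explain and that the primary model leaves out. It cannot deal with missingness that still depends on the 12-week PANSS itself once those variables are taken into account. An example is a participant who deteriorates after baseline and for that reason does not attend. Participants know their allocation (section 1, Blinding), so such a process could differ between arms, and the sample size section allows for 20% loss.

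If the two analyses agree, a reader may take that as evidence that the result is robust to missing data in general. The agreement would bear only on the choice of conditioning variables.

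**Working it through.** **Inputs from the SAP (section 1, Sample size).** Target difference 6 points, SD 15, baseline-endpoint correlation 0.6, two-sided 0.05, 80% power, 63 per group, 20% loss, 85 recruited per group.

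**Inputs assumed here.** Delta is the number of PANSS points by which missing participants are worse than missing at random predicts. The SAP gives no such figure, so a range is shown. The arithmetic concerns the 12-week comparison alone.

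**1. The SAP's own figure.** The baseline-adjusted SD is 15 × √(1 − 0.6²) = 12. With the normal approximation this gives 63 per group (power 80.1%), so the stated figure reproduces. At 20% loss from 85 per group, 85 × 0.80 = 68 per group are observed. In total about 136 are observed and 34 missing.

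**2. Shift in the treatment difference.** With missing fraction f and departure delta in each arm:

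shift = f(Actissist) × delta(Actissist) − f(ClinTouch) × delta(ClinTouch)

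| Delta, Actissist only | Shift at 20% missing | Share of 6 points | A 6-point benefit becomes |
|---|---|---|---|
| 3 | 0.6 | 10% | 5.4 |
| 5 | 1.0 | 17% | 5.0 |
| 10 | 2.0 | 33% | 4.0 |
| 15 | 3.0 | 50% | 3.0 |

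With 20% missing and the same delta in both arms, the shift is 0.20 × delta − 0.20 × delta = 0.

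**3. Where significance would be lost (departure in Actissist only).** The standard error is 12 × √(2/68) = 2.06, and the significance threshold is 1.96 × 2.06 = 4.03 points. The tipping delta is (estimate − 4.03)/0.20:

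- estimate 6.0: about 9.8 points
- estimate 5.0: about 4.8 points
- estimate 4.5: about 2.3 points

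These figures ignore any extra variance from imputation.

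**4. Whether the planned analysis would notice.** A simplified simulation used 170 participants, a 12-week outcome only, about 20% missing depending on one baseline variable, and 1,500 trials per delta. Outcomes of missing Actissist participants were made worse by delta, and the SAP's p < 0.05 rule was applied. Mean estimates:

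| Delta | Primary | Planned sensitivity | True effect, all randomised |
|---|---|---|---|
| 0 | −5.99 | −5.99 | −6.00 |
| 5 | −5.90 | −5.90 | −5.03 |
| 10 | −6.03 | −6.03 | −4.07 |
| 15 | −6.07 | −6.08 | −3.09 |

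The two analyses agree while both are off by about 1 to 3 points. The baseline variable was set up to be unrelated to the outcome, so close agreement is partly built in. The simulation illustrates the mechanism and does not predict this trial's result. The variable was not selected in about 30% of runs, and in those runs the two analyses were identical.

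**5. The selection rule.** With 34 missing and 136 observed, one predictor must differ by about 2.80 × √(1/34 + 1/136) = 0.54 SD to be selected with 80% probability. This describes a single predictor. It is not the chance that none of several is selected.

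**The case against.** **The SAP does not claim to test departures from missing at random.** It promises different assumptions and then states openly which one it uses. Missing at random given a larger set of variables is a different assumption from the primary one, and the check has some value. This stands. A reader might infer that the paragraph contradicts itself, but the text does not support that. The aim is broader than the method, and the method is openly described.

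**Identity with the primary analysis is possible but not shown to be usual.** A reader might infer from the 0.54 SD figure that often no covariate will be selected. The candidates are not listed, so this cannot be established. Section 2 lists about 19 secondary scores apart from ASSIST, counting both TLFB recall periods. If all 19 were screened, none predicted attendance and the tests were independent, the chance of selecting none would be 0.95^19, or about 38%. Correlated scores would raise it and real predictors would lower it. The main point does not depend on this, because the analysis remains missing at random whether or not covariates enter.

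**Stopping the app is not the same as a missing PANSS.** Section 3 keeps participants who do not complete therapy and commits to following up everyone in both arms, and PANSS could be collected by telephone. Disengagement could also occur under ClinTouch. This weakens disengagement from the app as a route to missing primary data. Missingness through unobserved deterioration remains possible.

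**The shifts shown are the unfavourable case.** They require all missing Actissist participants to be worse by delta on average, with no departure under ClinTouch. A full 6-point result tips only at about 9.8 points, roughly 0.8 of the adjusted SD of 12. This also stands, and it is why the deltas should be varied by arm. Results nearer 4 points tip much sooner.

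**Conclusion.** The point holds in a limited form. Both the primary analysis and the only missing-data sensitivity analysis assume missing at random, and no analysis in the SAP examines missingness that depends on the unobserved 12-week PANSS. The planned check can show only whether the conditioning set matters.

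The possible size is 1 or 2 points (17% or 33% of the 6-point target) for deltas of 5 or 10. This rests on the planned 20% loss and on assumed departures in one arm only. It falls to zero if the departures and the missingness are equal in both arms. A reader might take these figures as an estimate of bias in the trial. They are not, because the SAP reports neither the actual amount of missing 12-week PANSS nor anything about the outcomes of those not seen.

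The primary model is not at fault and need not change. The gap lies in how far its robustness can be judged, and it is inexpensive to close.

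**What to change.** In section 5, Sensitivity analysis:

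1. Keep the covariate analysis, and describe it as a check of the variables on which missing at random is conditioned.
2. Add a pre-specified delta-adjusted (tipping-point) analysis of 12-week PANSS. Impute missing values under missing at random, using the variables of the primary model and the 24-week PANSS where observed. Then make the imputed values worse by 0 to 10 points, or further until the conclusion changes. Do this in the Actissist arm only, the ClinTouch arm only and both arms.
3. Report the estimate and confidence interval across the whole range, and the delta at which the conclusion changes.

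The cost is one SAP paragraph and a short multiple-imputation script. It needs no new data and no change to the primary analysis. The one downside is that the delta range is a judgement, which is handled by showing the full range.

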### **COVID-19 pandemic**

Actissist 2.0 Statistical Analysis Plan v1.0

In light of the COVID-19 pandemic and the actions to mitigate the spread of the coronavirus, these actions may have an effect on the data collected in the Actissist 2.0 trial from March 2020 onwards. Recruitment had ceased by this date and all 12 week follow-ups had been completed. Therefore, the only data that could feasibly be impacted by the COVID-19 actions are the 24 week outcome measures of the remaining 21 participants.

We will perform an independent samples t-test comparing the 24 week PANSS outcome between the participants whose PANSS was collected before 1st March 2020, and those participants collected after 1st March 2020. If there are significant differences in the mean scores, we will conduct a sensitivity analysis for the intention-to-treat analysis by excluding participants with 24 week follow-ups collected after 1st March 2020.

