## 5. Statistical methods for inferential analysis

#### Analysis of primary and secondary outcomes

The primary and secondary outcomes, with the exception of the proportion of cannabis free days, will be analysed using a linear mixed-effects models with outcome measurement (at the two follow-up time points) as the dependant variable. The model will include fixed effects for timepoint, treatment, timepoint by treatment interactions, the baseline measure of the outcome, assuming a linear relationship between baseline and outcome, and service (2 categories: i) early intervention; ii) community mental health). Observations will be clustered by participant with an unstructured correlation matrix for the residuals. The model will be fitted using restricted maximum likelihood (19).

For each outcome and timepoint we will report the treatment effect estimate as the adjusted mean difference between groups, its standard error, 95% confidence intervals and p-value.

In addition, we will report estimates for Cohen's D effect sizes as the adjusted mean difference of the outcome divided by the sample standard deviation of the outcome at baseline. Confidence intervals for Cohen's D will be calculated by dividing the confidence limits by the sample standard deviation of the outcome at baseline. These will be displayed in a Forest Plot with the primary outcome at the top, followed by secondary outcomes.

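### The COVID-19 sensitivity analysis is gated by a weak, arm-pooled t-test that cannot show whether the 24-week treatment effect was disturbed and, read literally, drops unaffected 12-week data

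*SAP*

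**What the plan says.** The SAP section on the COVID-19 pandemic first limits the problem. By March 2020, "Recruitment had ceased by this date and all 12 week follow-ups had been completed", so "the only data that could feasibly be impacted by the COVID-19 actions are the 24 week outcome measures of the remaining 21 participants".

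It then sets a gate: "We will perform an independent samples t-test comparing the 24 week PANSS outcome between the participants whose PANSS was collected before" 1 March 2020 and those whose PANSS was collected after it. No significance level is given for this test, and it has no term for treatment arm or baseline PANSS.

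The consequence follows: "If there are significant differences in the mean scores, we will conduct a sensitivity analysis for the intention-to-treat analysis by excluding participants". The participants meant are those with a 24-week follow-up after that date. If the test is not significant, no further check is planned.

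Two other sections matter here. Under Primary outcome, "The primary outcome is psychotic symptoms measured by PANSS total score at 12 weeks post randomisation". Under Analysis of primary and secondary outcomes, the intention-to-treat analysis uses "linear mixed-effects models with outcome measurement (at the two follow-up time points) as the dependant variable", so each participant contributes a 12-week and a 24-week row to one model (Appendix 1 confirms the long format).

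**The concern.** The gate raises two problems and the exclusion a third.

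- **Power.** With at most 21 people in one group, a non-significant result is weak evidence that nothing happened, yet it ends the inquiry.
- **Target.** The trial estimates a difference between arms, adjusted for baseline and service. The gate compares calendar periods with the arms pooled. A shift common to both arms leaves the treatment effect alone but can trip the gate. A shift that differs by arm disturbs the treatment effect but may largely cancel in the pooled mean. Later participants may also differ from earlier ones for reasons unrelated to the pandemic.
- **Unit of exclusion.** The section says that only 24-week measures could be affected, then excludes participants. In a model that holds both follow-up rows, this also removes their 12-week primary outcomes.

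At stake is whether the reader of the 24-week results gets a usable robustness check, and whether that check, when run, blurs the 12-week result for no reason.

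**Working it through.** **Inputs from the SAP.** SD 15, target difference 6 points, baseline-endpoint correlation 0.6, two-sided 0.05, 63 per group for 80% power, 20% loss, N = 170 (all under Sample size). At most 21 late participants (COVID-19 section).

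**Assumptions.** The gate uses two-sided 0.05. SD 15 also holds at 24 weeks. Total completers are 126 (2 × 63), 136 (170 × 0.8) or 170, so there are 105, 115 or 149 earlier participants. The 21 split 10/11 by arm.

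**Step 1: the plan's own figure.** Baseline-adjusted SD = 15 × √(1 − 0.6²) = 12. Then n per group = 2 × (1.960 + 0.842)² × 12² / 6² ≈ 62.8, so 63. The SAP's figure is reproduced.

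**Step 2: power of the gate for a common shift.** SE = 15 × √(1/21 + 1/n₂), with power from the noncentral t distribution on 21 + n₂ − 2 degrees of freedom.

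| Earlier participants n₂ | SE | Power, 3 points | Power, 6 points | Shift with 80% power |
|---|---|---|---|---|
| 105 | 3.59 | 0.13 | 0.38 | 10.1 |
| 115 | 3.56 | 0.13 | 0.39 | 10.0 |
| 149 | 3.50 | 0.14 | 0.40 | 9.9 |

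The assumed number of completers hardly matters, because the 21 set the limit. If only 15 to 17 of the 21 attend, power for 6 points is 0.30 to 0.34 and the 80% shift is about 11 to 12 points.

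**Step 3: what the gate responds to.** 20,000 simulated trials per scenario, 21 later against 115 earlier participants, SD 15:

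| Shift among late participants (arm A, arm B) | Change in their treatment effect | Gate fires |
|---|---|---|
| 0, 0 | 0 | 5% |
| +6, +6 | 0 | 39% |
| +10, +10 | 0 | 80% |
| +6, 0 | 6 points | 12% |
| +6, −6 | 12 points | 5% |

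The gate fires most often where the treatment effect is intact, and at about its false-positive rate where the effect among these participants has moved most.

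**Step 4: cost of excluding participants at 12 weeks.** SE = 12 × √(4/N), with and without 21 participants.

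| Completers | SE, all | SE, less 21 | Ratio | Power for 6 points |
|---|---|---|---|---|
| 126 | 2.14 | 2.34 | 1.10 | 0.80 → 0.73 |
| 136 | 2.06 | 2.24 | 1.09 | 0.83 → 0.76 |
| 170 | 1.84 | 1.97 | 1.07 | 0.90 → 0.86 |

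These losses occur only inside the sensitivity analysis. Dropping only the late 24-week rows leaves the left-hand 12-week figures in place.

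**Step 5: how far the 24-week effect could move.** A change of Δ in the treatment effect among the 21 moves the overall 24-week effect by roughly Δ × 21/N. With Δ = 6 this is 1.0, 0.9 or 0.7 points for N = 126, 136 or 170. With Δ = 12 it is 2.0, 1.9 or 1.5. The corresponding standard errors, if the Sample size figures also hold at 24 weeks, are 2.14, 2.06 and 1.84.

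**The case against.** A reader might infer that a significant gate changes the trial's 12-week primary estimate. The SAP does not support that: the exclusion belongs to an added sensitivity analysis, and the intention-to-treat analysis on all available data stands.

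A reader might also take it as settled that 21 primary outcomes are discarded. That is the literal reading. The section speaks of 24-week measures throughout, so the authors may have meant to drop only the 24-week comparison for these people. Twenty-one is also an upper limit, since anyone who missed the late 24-week visit would not be excluded and not all of them need have 12-week data. What stands is that the text says participants, and the model contains both rows.

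Six points is the sample-size target for the difference between arms, not a pandemic shift the SAP undertakes to detect, and a common shift of about 10 points would be caught about 80% of the time. That is fair, but it does not answer the second problem: larger common shifts still say nothing about the treatment effect.

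The subgroup analysis by recruitment period, under Accounting for versions of Actissist, does test whether the effect varies between earlier and later recruits. Its periods follow app versions rather than 1 March 2020, so it is not a substitute.

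The strongest objection is materiality. The 24-week outcome is secondary, and by Step 5 a missed disturbance of these sizes would move it by about 1 to 2 points, at most about one standard error. This stands and limits the severity.

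**Conclusion.** The concern holds, as a minor point. The gate cannot show whether the 24-week treatment effect was disturbed: its power is about 0.4 for a common 6-point shift, and it fires at about 5% when the arms move 6 points in opposite directions. As literally written, the exclusion contradicts the section's own statement that 12-week data are unaffected, at a cost of up to 21 outcomes and a 7 to 10% larger 12-week standard error within that sensitivity analysis.

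The figures rest on the SAP's SD and correlation, an assumed gate level of two-sided 0.05, and 126 to 170 completers. The issue is confined to a supplementary check on a secondary time point.

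**What to change.** Delete the t-test. Always run one sensitivity analysis with the same mixed model, setting to missing only the 24-week observations collected from 1 March 2020 and keeping the 12-week rows of those participants. Assign 1 March itself explicitly, because the current text covers only dates before and after it.

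The long data format allows this directly. The model's missing-at-random assumption, conditional on baseline and the other follow-up, lets the retained 12-week values inform the 24-week estimate.

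Do not replace the gate with a treatment-by-period test. With 10 and 11 late participants per arm, its standard error would be about 5.6 to 7.2 points and its power for 6 points only 0.13 to 0.19.

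The cost is a short change of wording, one extra model run and a slightly less precise 24-week estimate in the sensitivity analysis. A data-dependent decision is removed.
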